4.2.6 Proteinuria 2+ or greater by urine dipstick

4.2.7 Signs or symptoms suggestive of acute HIV infection

4.2.8 Any other reason or condition that in the opinion of the investigator would interfere with participation, complicate interpretation of study outcome data, or otherwise interfere with achieving the study objectives.

4.3 Enrollment Procedures

4.3.1 Prior to implementation of this protocol, sites must have the protocol and consent form approved by their local institution review board (IRB). Sites must be registered with and approved by the CCTG Data Center. Site registration must occur before any subjects can be enrolled in this study.

4.3.2 Once a candidate for study entry has been identified, details will be carefully discussed with the subject. The subject will be asked to read and sign the consent form that was approved by both the local IRB and the CCTG Data Center.

4.3.3 A patient identification number (PID) will be assigned to each patient screened for the study. PIDs will include site code and be formatted to be compatible with the BIT data core. PIDs will not be reassigned even if the subject fails to enter the study. The PID must be included on every CRF and subject specimen during the study. Each site must maintain a master list of PIDs in a central location. The patient registration and inclusion/exclusion CRF must be completed on the online system.

5.0 STUDY TREATMENT

5.1 Regimens, Administration, and Duration

5.1.1 Regimens

Subjects will be randomized 1:1 to one of the two treatment arms:

ARM A: FTC/TDF 200/300 mg fixed dose combination once daily + iTAB

ARM B: FTC/TDF 200/300 mg fixed dose combination once daily

- ♦ Use of the FTC/TDF fixed dose combination is not allowed if the CrCl is <50 mL/min, which should be confirmed within 7 days. TDF/ FTC should be discontinued if confirmed.

5.1.2 Administering and Dispensing

Emtricitabine/tenofovir disoproxil fumarate fixed-dose combination containing 200 mg of emtricitabine and 300 mg tenofovir disoproxil fumarate will be administered orally as one tablet once daily with or without food.

Enough study product should be dispensed to last until the subject's next scheduled visit.

5.1.3 Duration

Subjects will participate in this study until 48 weeks beyond the enrollment of the last subject with a maximum duration of 96 weeks for any subject. Subjects may receive study treatment until their last study visit.

Subjects will receive study treatment for the duration of the study unless they meet criteria for discontinuation.

5.2 Study Product Formulation

Emtricitabine/tenofovir disoproxil fumarate (FTC/TDF, Truvada®): 200 mg/300 mg coformulated tablet. Store at 25°C (77°F); excursions permitted to 15°-30°C (59°-86°F) [see USP Controlled Room Temperature].

5.3 Pharmacy: Product Supply, Distribution, and Accountability

5.3.1 Study Product Supply/Distribution

Emtricitabine/tenofovir disoproxil fumarate will be supplied by Gilead Sciences through the UCSD/AVRC Research Pharmacy and distributed to all sites.

The site pharmacist can obtain study product for this protocol by following the instructions in the CCTG-595 Pharmacy Manual.

5.3.2 Study Product Accountability

The site pharmacist is required to maintain complete records of all study product received from the UCSD /AVRC Research Pharmacy. All unused study product must be returned to the sponsor (or as otherwise directed by the sponsor) after the study is completed or terminated. The procedures to be followed are provided in the CCTG-595 Pharmacy Manual.

5.4 Concomitant Medications

Whenever a concomitant medication or study agent is initiated or a dose changed, site investigators must review the concomitant medications and study agent's most recent package inserts, Investigator's Brochures to obtain the most current information on drug interactions, contraindications, and precautions.

5.4.1 Prohibited Medications (Refer to Section 4.2 for addition information on prohibited medications).

5.4.1.1 All investigational drugs

5.4.1.2 All HIV vaccines

5.4.1.3 Any immunomodulators

5.4.1.4 Systemic cytotoxic chemotherapy

5.4.1.5 All other antiretroviral medications (excluding FTC/TDF given as PEP or PrEP)

5.4.1.6 Drugs with known nephrotoxicity

Subjects must have discontinued prohibited medications at least 30 days prior to entry.

5.5 Adherence Assessment

Throughout the study, the documentation of adherence to study drug is essential. The adherence questionnaire will be completed during each study visit. This will include the ACTG 4-day adherence questionnaire as well as the VAS over the previous 4 week period, except for the week 4 visit where adherence will be assessed since starting medication.

6.0 CLINICAL AND LABORATORY EVALUATION

6.1 Schedule of Evaluation

Schedule of Evaluations	Screen	Study Weeks of Follow-up								Suspected HIV/STI infection ⁴	Interim for Missed Visit ⁵
	Within 30 days	0	4	12	24 or 72	36 or 60 or 84	48 or 96	End of Study or premature D/C	Post-study, 3-month		
Visit Window		± 14 days									
Informed Consent	X										
Medical/Medication History	X										
Documentation of HIV status by rapid HIV test plus NAT or Ag/Ab combo assay	X										
Randomization		X									
Pre/Post Assessments ¹		X						X			
iPAD self-administered survey ²		X	X	X	X	X	X	X		X	X
Risk reduction Counseling		X	X	X	X	X	X	X		X	X
Review PrEP adherence (ACTG 4 day and VAS)			X	X	X	X	X	X		X	X
Clinical Hx of STI and PREP use		X	X	X	X	X	X	X		X	X
Assessment of adverse events		X	X	X	X	X	X	X		X	X
Targeted exam (as clinically indicated)	X	X	X	X	X	X	X	X		X	X
Concomitant medications		X	X	X	X	X	X	X		X	X
Dispense TDF/FTC (if HIV rapid test negative)		X	X	X	X	X	X				X
Calcium and vitamin D intake						X ⁶					
Phone call follow-up									X		

Schedule of Evaluations	Screen	Study Weeks of Follow-up							Post-study, 3-month	Suspected HIV/STI infection ⁴	Interim for Missed Visit ⁵
	Within 30 days	0	4	12	24 or 72	36 or 60 or 84	48 or 96	End of Study or premature D/C			
Laboratory											
CBC/Chemistry	X										
Calculated GFR (serum Cr)	X		X	X	X	X	X	X			X
Urine Dipstick	X		X	X	X	X	X	X			X
Rapid HIV Test		X	X	X	X	X	X	X		X	X
STI testing- throat, rectum, urine; blood RPR		X			X		X	X		X	X
Rectal swab (x2)		X			X ⁷		X ⁷				
HBsAg-/HBsAB-/HBcAB	X										
If HBsAg-/HBsAB-/HBcAb+, Hepatitis B DNA PCR	X										
HIV RNA, CD4, HIV genotype, banked PBMC		X ³	X ³	X ³	X ³	X ³	X ³	X ³		X ³	X ³
Plasma banked specimen		X	X	X	X	X	X	X		X ³	X
Banked clotted blood		X									
Dried blood spot				X	X	X	X	X		X ³	X
Urine for storage		X	X	X	X	X	X	X		X	X
¹ Pre: attitudes toward safe sex, disclosure, access to care, social support, texting ability, Kalichman sexual compulsivity; Post: satisfaction with iTAB; Pre/Post: HIV literacy, stigma and disclosure, AUDIT, DAST-10 ² includes: risk behavior, adherence assessments, intention to adhere, PHQ9, SCID substance use screen ³ Perform if HIV+ ⁴ Any time history or symptoms suggest potential HIV or STI, check with study MD for appropriate test ⁵ Subjects may have an interim visit if past window of scheduled visit, next visit should be back to regular schedule ⁶ To be performed at week 36 only ⁷ Performed only once on or after Week 48 coinciding with STI screening (Week 48, 72, or 96)											

6.2 Definitions for Schedule of Events and Timing of Evaluations

6.2.1 Screening Assessments

Occur prior to the subject taking any study medications, treatments, or interventions

Patient Registration: A patient identification number (PID) will be assigned to each patient screened for the study. PIDs should not be reassigned even if the patient fails to enter the study. The PID must be included on every CRF and patient blood sample. Each site must maintain a master list of PIDs in a central location. The patient registration and inclusion/exclusion CRF must be completed on the online system.

All subjects interested in screening for the PrEP project will sign an informed consent document that had been approved by local IRB at the site. Screening procedures (see schedule of evaluations) will include: determination of inclusion and exclusion criteria; confirmation of HIV status and screen for acute HIV symptoms. HIV serology will be performed as part of screening, including rapid HIV test and NAT or equivalent (antigen antibody test). Laboratory screening will include CBC, chemistry values, GFR (Cockcroft-Galt) LFT and HBsAg. If a subject qualifies and signs consent the window to complete the baseline assessment and start PrEP will be two weeks.

6.2.2 Entry Evaluations (day 0)

Randomization: subjects that meet all the inclusion and exclusion criteria will be randomized at their day 0 entry visit. Subjects will be randomized to receive standard of care or the iTAB adherence intervention, stratified by site. Subjects randomized to the iTAB intervention will set up the customized text message stems and enter the timing of the text message reminders; the information will be entered in the online iTAB system by the study coordinator.

At baseline all subjects will receive HIV transmission risk reduction counseling by a health educator and detailed information about the use of PrEP, including the risks, potential adverse events and the critical importance of drug adherence.

6.2.3 On-Study Evaluations

After counseling, laboratory testing and randomization, participants will receive sufficient TDF/FTC study medication to last until the next scheduled visit (either 4 or 12 weeks) through the investigational pharmacy. Medication renewals will not be available if a subject misses a scheduled appointment. An informational pamphlet on TDF/FTC will be provided that will summarize the label package insert information for patients (in English or Spanish) with changes made to tailor the information for someone that is not HIV infected. Participants will be directed to take one pill once a day at a convenient routine time. If there are missed doses, participants will be told to take the next scheduled dose on time and not to take any additional pills to catch up. Bottles with any remaining missed doses will be returned to the pharmacy at the time of medication renewal and the number of untaken doses will be recorded. At each clinic visit, TDF/FTC medication adherence will be

reviewed by the clinician, adverse events will be queried and adherence and barriers to adherence will be discussed. All subjects will receive episodic adherence counseling within the confines of routine clinic visit. Each clinic visit will also include blood draw for calculated GFR (serum creatinine) and plasma FTC drug levels, and HIV testing. STI testing including NAT screening for GC and chlamydia from throat and rectal swabs and from urine and RPR from blood will be done at week 0 and every 24 weeks thereafter.

Adherence and Behavioral Assessments

We will measure adherence using the ACTG medication adherence questionnaire [25]. At each follow-up visit, the ACTG four-day questionnaire will be administered using the web-based data capture system. The instrument tracks the number of doses skipped over the past four days and reasons why medications may have been skipped. In addition, we will ask their ability to adhere by Likert scale and use the Visual Analog Scale (VAS), which appears as an ordinal scale representing the percent of medication taken relative to that which has been prescribed over the past 4 weeks. Subjects are presented with a line anchored at 0% and 100% and are asked to mark a line on the scale indicating their own PrEP adherence [26].

In the standard study visit, the coordinator will perform HIV testing and blood work, review test results, provide TDF/FTC prescriptions, discuss medication use, adherence, risk reduction and troubleshoot any barriers. The standard behavioral survey will include assessment of TDF/FTC adherence, HIV transmission risk behaviors, substance use, depression scores and other risk behavior details (e.g. sexual partnerships, sexual acts, condom use).

Laboratory Safety Assessments

At follow-up clinic visits, all participants will have a blood drawn for creatinine clearance estimates. A rapid test for HIV will be performed. HIV test results will be provided during the clinic visit. If there are grade 3-4 adverse events (thought to be related to study medication- see toxicity section) or HIV seroconversion is detected, the participant will be called to discontinue TDF/FTC and to come to the clinic as soon as feasible. Any positive rapid test will be confirmed by Western Blot and HIV RNA; CD4 cell count and an HIV genotype for drug resistance will be done. Newly diagnosed HIV subjects will be counseled and be linked to HIV clinical care within the existing clinic or to another provider

designated by the participant. All PrEP-related clinic visits, laboratory testing and TDF/FTC medication will be provided by the study without charge to the subject.

FTC Qualitative Plasma Concentration as an Adherence Marker:

Plasma will be drawn at every visit starting at week 4 for FTC concentrations. Samples will not be run in real time and will not be available for clinical use.

Chlamydia, gonorrhea and syphilis testing

Subjects will have day 0 and every 24-week assessment to include urine and swabs from the rectum and throat for NAT testing for Chlamydia and gonorrhea. Blood will be drawn for RPR. In between visits, subjects will be told to come to the study nurse if they experience symptoms of an STI. They will also be asked if they were tested elsewhere between visits. All new STI cases will be referred to their provider or the Department of Health for treatment. They will be given a card to have filled out documenting treatment given, which they will be asked to bring back to their next study visit. All new STI cases will also be counseled on the need for partner therapy and will suggest that they receive assessment and treatment or partner delivered therapy. STI testing can also occur as an interim visit for high-risk exposure or symptoms suggestive of new STI.

Sexual Risk Counseling

Standard of care HIV risk reduction counseling will be providing to all participants consistent with pre- and post-test counseling for persons receiving community HIV testing. The study will provide streamlined in-person risk reduction counseling at each visit that will use the RESPECT paradigm of focusing on a single risk behavior as identified by the subject. The goal of brief and targeted counseling is to help the individual to identify his most significant risky behavior and to implement concrete actions to decrease the specific risk behavior until the next study visit. Participants will undergo this process at each visit.

6.3 Special Instructions and Definitions of Evaluations

6.3.1 Documentation of HIV infected status at screening

The lack of HIV-1 infection will be documented by any licensed screening antibody (rapid test plus NAT or Ab/Ag) test. A positive HIV test will be confirmed by a second EIA , Western Blot, or HIV RNA viral load.

6.3.2 Medical and Laboratory History

At screening, a medical history will be obtained and will be recorded in the source documents. The medical history should include any previous illnesses that might be consistent with acute HIV infection, history of STI and other routine medical conditions.

6.3.3 Medication History

At screening, a medication history (only of those taken within the last 30 days prior to entry) with actual or estimated start and stop dates will be obtained and recorded in the source documents and the concomitant medication CRF, including:

- ◆ All prescription medications.
- ◆ Non-prescription medications.
- ◆ Alternative therapies and/or dietary supplements.
- ◆ Allergies to any medications and their formulations must be documented.

6.3.4 Concomitant Medications

During study visits all antibiotics and other concomitant medications taken since the last visit will be recorded in the source documentation and entered into the concomitant medication log CRF.

6.3.5 Study Drug Modifications

No modifications of PrEP regimen will be allowed on this study. TDF/FTC may be temporarily held for adverse events as per section 7. TDF/FTC should be discontinued if any criteria for stopping are met (see discontinuation section). Discontinuation will be documented on the TDF/FTC discontinuation CRF.

6.3.6 Clinical Assessments

Targeted Physical Exam

A targeted physical examination will be based on any signs or symptoms previously identified that the subject has experienced within 30 days of entry or since the last visit. This examination will be performed at all visits when indicated. Documentation must include any symptoms consistent

with acute HIV infection.

Height and Weight

Height and weight will be measured at study entry.

Signs and Symptoms

All signs, symptoms, toxicities and deaths will be documented in the subject's record. At entry, all signs/symptoms experienced within 30 days of entry will be recorded on the CRFs. For all other visits including a suspected HIV infection visit, all Grade > 1 signs and symptoms will be recorded on the CRFs that have occurred since the last visit. Any signs or symptoms that lead to a change in treatment, regardless of Grade, will be recorded on the CRF. The source document will include date of onset and date of resolution, but the CRF will only record prevalence of a given adverse event since the previous study visit.

Refer to the ACTG Table for Grading Adult Adverse Experiences.

Diagnoses

The following should be recorded on the CRFs: HIV and STI diagnoses, malignancies, new medical conditions and death. The source document must include date of diagnosis and date of resolution.

6.3.7 Clinical Assessments for Detected STI

At all visits ask if the participants if they have had an STI in the interim, current symptoms.

6.3.8 Laboratory Evaluations

Record all designated laboratory values on the CRFs throughout the course of the study. All baseline values, regardless of toxicity, for specific laboratories will also be recorded on the laboratory CRF including: WBC, neutrophil count, hemoglobin, platelets, creatinine with estimated GFR (Cockcroft-Galt formula), glucose, AST/ALT, alkaline phosphatase and total bilirubin. All values of creatinine with estimated GFR (Cockcroft-Galt Formula) will be recorded in the CRF and performed as per the SOE.

Any laboratory toxicities that lead to a change in treatment, regardless of Grade, will be recorded on the adverse event CRF.

Refer to the Division of AIDS Table for Grading Adult Adverse Experiences.

6.3.9 Urinalysis
A dipstick urine test will be done at screening and every visit after day 0. Protein, glucose and leukocyte esterase will be recorded in the CRF.

6.3.10 T-cell counts and Virology tests

Plasma HIV-1 RNA

An HIV-1 RNA viral load will be performed at the site's local laboratory within 7 days of a new positive antibody test or NAT.

An HIV drug resistance test should be performed with detectable viral load of greater than 500 copies/mL.

CD4 T-cell enumeration will be performed to obtain absolute CD4+/CD8+ count and percentages within 7 days of new HIV diagnosis.

6.3.11 *Stored Plasma and other specimens*

Stored plasma will be collected at day 0, at all visits and with any new HIV diagnosis.

*Specimens will be stored at the site's local laboratory and batched shipped to the central laboratory (UCSD) after completion of the study.

6.3.12 *Pharmacokinetic Studies*

At each visit, record the time and date of the last 3 doses of TDF/FTC medication in the CRF. Dried blood spots will be stored at -80 at each visit beginning at Week 12 for possible future use for plasma and intracellular TFV and FTC pharmacology.

6.3.13 *Questionnaires*

At each visit, the subject should complete the self-reported questionnaires.

6.3.14 *Rectal swabs*

At day 0 and at one additional time point on or after Week 48, all subjects will have a rectal swab stored for possible future studies of the gut microbiome. These tests will be done in retrospect and not available for the subjects.

6.3.15 At day 0, all subjects will have blood stored for future use to examine host DNA. Subjects will sign a consent that informs them of the storage of material for possible host genomic testing.

6.3.16 Participants will be asked to recall food items eaten over the last 3 days at the week 36 visit. The calculator used in the ACTG 5280 study, which is adopted from the USDA database, will be used to quantify vitamin D and calcium intake (see Appendix VI).

6.4 Schedule of Evaluations for Subjects On-Study, Off-Medications

6.4.1 At any point, subjects may elect to stop study medications but remain on study. Subjects that stay on study but stop medications will not be allowed to resume again.

Subjects will follow the same schedule as defined in Section 6.1 until the end of study. Study medications will not be dispensed at clinic visits, and evaluations related to counseling or monitoring of medications (including urine dipstick and serum creatinine) will not be performed. These include Adherence and Risk-reduction counseling and collection of dried blood spots. If the subject was randomized to the iTab arm, their account will be switched to “inactive.”

STI and HIV rapid test screenings and questionnaires will still be administered as the schedule dictates.

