enrollment of non-African Americans will be capped at 85% of 400 subjects (340) to achieve at least 15% African Americans. If 340 non-African American subjects are enrolled, then enrollment for this subgroup will stop and the study will remain open only for African Americans.

3.2 iTAB Adherence Intervention

This proposal will perform a study of potential methods to improve adherence and retention by evaluating standard procedures versus the use of the iTAB platform. All subjects will receive SoC that will include health education, clinical assessments, laboratory safety monitoring, STI and HIV screening, HIV risk reduction counseling, assessment of psycho-social barriers, adherence counseling, and completion of a computer based survey.

Subjects will be randomized to 1) SoC clinic visits as outlined in section 6.0 and 2) SoC visits plus support using text messaging through the iTAB system. Subjects assigned to the iTAB intervention will have visits with the study coordinator to introduce the iTAB texting system, discuss contact information to assist in recovering the subject if they miss appointments and provide training on iTAB framework for texting supportive reminder messages and tracking adherence. The study will provide subject reimbursement to pay for unlimited text message use and in cases where a subject does not have a phone, the appropriate cell phone will be provided.

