4.0 SELECTION AND ENROLLMENT OF SUBJECTS

4.1 Main Study Inclusion Criteria

- 4.1.1 Man or transgender M to F who has sex with men.
- 4.1.2 Age 18 years or older.
- 4.1.3 Subjects must have substantial ongoing risk of acquisition of HIV as evident by one or more of the following:
 - ♦ Has at least one HIV infected sexual partner for ≥ 4 weeks.
 - ♦ No condom use during anal intercourse with ≥ 3 male sex partners who are HIV-positive or of unknown HIV status during the last 3 months
 - ♦ No condom use during anal sex with ≥ 1 male partner and STI diagnosis during the last 3 months
- 4.1.4 Negative for HIV infection by rapid HIV test and confirmed negative by NAT or other sensitive method such as antibody- antigen test.
- 4.1.5 Acceptable laboratory values in the past 30 days:
 - ♦ Calculated creatinine clearance of at least 60 mL/min by the Cockcroft-Gault formula (eCcr (male) in mL/min = $[(140 - \text{age in years}) \times (\text{lean body weight in kg})] / (72 \times \text{serum creatinine in mg/dL})$)
 - ♦ Alanine aminotransferase (ALT) and/ or aspartate aminotransferase (AST) < 3 x upper limit of normal (ULN)

- ◆ Hemoglobin > 9 g/dL
- ◆ Absolute neutrophil count > 750/ mm³
- ◆ Platelets > 75,000/ mm³

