7.1 General Management for Grade 1-4 Events

7.1.1 Grade 1 or 2

Subjects who develop a Grade 1 or 2 adverse event or toxicity may continue TDF/FTC without alteration of the dosage, except as noted below. Persistent grade 1 or 2 toxicity should be discussed with the protocol team. Those subjects experiencing Grades 1 or 2 adverse events which results in discontinuation of the TDF/FTC should continue to be followed on study, but off study medication.

7.1.2 Grade 3

Management of Grade 3 toxicities should be discussed with the protocol team via email. Please refer to the subsequent sections for management of specific events.

In the event that a subject develops a **symptomatic** Grade 3 reaction considered to be TDF/FTC-related, the study drug should be discontinued and the subject should be followed weekly until resolution of the adverse event. Once Grade 3 is resolved the subject should be followed on-study, but off study medication. For subjects with asymptomatic Grade 3 toxicity or laboratory abnormalities, the protocol team should be consulted for possible re-introduction of TDF/ FTC.

7.1.3 Grade 4

Subjects who develop a Grade 4 adverse event or toxicity judged to be TDF/ FTC-related will have the study drug permanently discontinued. For other Grade 4 events, if the toxicity or laboratory elevation is thought not to be due to TDF/FTC, TDF/FTC may be continued and laboratories repeated within 2 weeks (for example for asymptomatic elevation of CPK or triglycerides). If it is not possible for the investigator to discern another causative agent/ condition or if TDF/FTC could be the causative agent, then TDF/FTC must be discontinued. Subjects experiencing Grade 4 adverse events requiring permanent discontinuation of TDF/FTC therapy should be followed weekly until resolution of the adverse event. Once Grade 4 is resolved the subject should be followed on-study, but off study medication.

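### Protocol 6.4.1 drops scheduled risk-reduction counseling for participants who stop study PrEP but stay on study, although its content is sexual risk and HIV testing continues

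*Protocol*

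**What the plan says.** Protocol 6.4.1 covers people who choose to stop study medication but remain on study. They may not restart. They keep the 6.1 visit schedule, but drug is not dispensed and evaluations connected with the medication are left out. Of the omitted items it says: "These include Adherence and Risk-reduction counseling and collection of dried blood spots". Of what remains it says: "STI and HIV rapid test screenings and questionnaires will still be administered as the schedule dictates".

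The general rule is in Protocol 6.2.3, under Sexual Risk Counseling: "Standard of care HIV risk reduction counseling will be providing to all participants", in line with the pre- and post-test counseling of community HIV testing. On frequency: "The study will provide streamlined in-person risk reduction counseling at each visit". On content, the session works by "focusing on a single risk behavior as identified by the subject". Protocol 3.2 puts the same counseling in the standard-of-care package: "All subjects will receive SoC that will include health education, clinical assessments, laboratory safety monitoring, STI and HIV screening, HIV risk reduction counseling". Adherence counseling is a separate item in that list.

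**The concern.** Creatinine, urine dipstick, dried blood spots and adherence counseling lose their purpose when the drug stops. A session on sexual risk behavior does not. Section 6.4.1 treats it as if it did.

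The people affected entered under Protocol 4.1.3: "Subjects must have substantial ongoing risk of acquisition of HIV as evident by one or more of the following". After stopping they no longer receive study PrEP and cannot resume it. At the same point they lose the scheduled session on their main risk behavior, at visits they still attend and where they are still tested for HIV. What is at stake is participant care, not the treatment comparison.

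**Working it through.** The plan gives no figure to reproduce. The check sets the sections side by side and then counts visits.

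**1. Is the counseling a medication evaluation?** In 6.2.3 the session asks the participant to name the riskiest behavior and agree actions to reduce it before the next visit. Nothing in that requires drug. The 6.1 schedule agrees: it marks risk-reduction counseling at the end-of-study or premature-discontinuation visit and at the suspected HIV/STI visit, and marks TDF/FTC dispensing at neither. The protocol thus already schedules this counseling at visits where no drug is given.

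**2. Who is covered?**
- Elective stoppers: stated in 6.4.1.
- Toxicity stops: inferred from the 6.4 title together with 7.1.1, 7.1.2, 7.1.3, 7.2.2 and 7.2.5, which send discontinued participants to follow-up off drug. For Grade 4 events, for example: "Once Grade 4 is resolved the subject should be followed on-study, but off study medication".
- Not counted: rash (7.2.1), where the drug is held and permanent discontinuation is not stated, and holds that allow resumption (for example 7.2.7).

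**3. How many sessions are lost per person?** Follow-up visits fall at weeks 4, 12, 24, 36, 48, 60, 72, 84 and 96. For a stop at visit week s, with that visit's session still given, sessions lost = number of scheduled weeks w with s < w ≤ 48 (or ≤ 96).

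| Stop | Lost to week 48 | Lost to week 96 (maximum) |
|---|---|---|
| Before week 4 | 5 | 9 |
| Week 4 | 4 | 8 |
| Week 12 | 3 | 7 |
| Week 24 | 2 (36, 48) | 6 (36, 48, 60, 72, 84, 96) |
| Week 36 | 1 | 5 |
| Week 48 | 0 | 4 |

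The week-96 column is a maximum because follow-up ends 48 weeks after the last enrollment (5.1.3). The rapid HIV test is kept at every one of these visits. STI tests, every 24 weeks, are kept after a week-4 stop at 2 of the 4 visits to week 48 (weeks 24, 48) or 4 of the 8 to week 96 (adding 72 and 96).

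**4. How many people?** The documents do not say. As an illustration only, assume 2% to 10% of 400 stop and stay on study, all at week 24:
- People: 0.02 × 400 = 8 to 0.10 × 400 = 40.
- Sessions to week 48: 8 × 2 = 16 to 40 × 2 = 80.
- Sessions to week 96, at most: 8 × 6 = 48 to 40 × 6 = 240.

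**5. Does it touch the primary endpoint?** SAP section 6 uses dried blood spots from week 12 and the last on-drug visit. Counseling given after the drug stops cannot change either sample.

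**The case against.** The strongest reply is that this is ordinary drafting. Section 6.4.1 adopts the 6.1 schedule and then lists exceptions for one subgroup. In the same paragraph it overrides the every-visit rules for the urine dipstick (6.3.9) and dried blood spots (6.3.12), and nobody would call those contradictions. A site would know what to do. This stands: a reader might infer that 6.4.1 contradicts 6.2.3, but it is an explicit exception. What remains is whether the exception is well chosen.

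The grouping also has a rationale. The Schema describes risk-reduction counseling as part of access to PrEP, section 2.1 couples it with the adherence message, and 6.2.3 places it beside prescriptions in the standard visit. That explains the choice, but not why a sexual-risk session should end when the participant loses study PrEP.

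A reader might also infer that off-drug participants lose all counseling. The documents do not support that. Section 3.1 includes counseling with routine HIV testing in both arms, and 6.4.1 does not name test-related counseling among its omissions. Section 6.2.3 still provides partner-therapy counseling for new STI cases, and counseling and linkage to care for new HIV diagnoses. Section 6.4.1 also leaves unclear whether the session is dropped at suspected-infection and interim visits.

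Finally, some stoppers may be at lower risk (9.6.5 mentions lack of perceived risk), FTC/TDF taken as PrEP outside the study is not prohibited (5.4.1.5), and nothing in the documents shows that omitting these sessions changes HIV, STI or behavioral outcomes. These points limit the importance of the concern. They do not supply a reason for the omission.

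**Conclusion.** The point holds as a participant-care matter. Section 6.4.1 deliberately removes a scheduled sexual-risk session on a medication-related rationale that does not match the session's content, while HIV and STI testing go on. The size is 2 sessions to week 48, and at most 6 to week 96, for a stop at week 24. The total cannot be derived from the documents.

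Inclusion of toxicity stops is an inference from the section title and section 7; only elective stoppers are named. A reader might infer a threat to the trial's main result. There is none: the same rule applies in both arms and the SAP primary endpoint does not depend on it. This is a low-cost improvement for participant safety, not an error in the analysis plan.

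**What to change.** In Protocol 6.4.1, make two edits. Delete risk-reduction counseling from the omission sentence, so that it names only adherence counseling and dried blood spots. In the retention sentence, insert risk-reduction counseling (6.2.3) between the STI and HIV test screenings and the questionnaires. No SAP change is needed. If the sponsor prefers to keep the exception, it should give the reason and qualify the each-visit statement in 6.2.3.

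The cost is one short session at visits already held, plus an amendment with IRB review (12.1). A change during the study would give off-drug participants different counseling before and after the amendment. That could slightly shift later risk-behavior and STI results, which are secondary objectives (SAP 3.2). The rule would be the same in both arms, and recording the amendment date would let the analyst describe any shift.
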